- Miniscrew, 8 mm length x 1.6mm diameter TAD (Jeil).
- American Orthodontics Arch wires.
- American Orthodontics Molar bands/tubes.

D] Outcomes

[figure not shown]
Primary outcome: is to monitor the Duration of space closure during en-masse and two steps retraction. All outcomes will be assessed as the difference between T0 at the start of retraction and T1 after complete space closure.

Secondary outcomes: is to monitor the changes in the anterior teeth position (final anterior teeth tip, torque and vertical position), anchorage loss, presence of any root resorption and pain associated with the different methods used for retraction.

E] Participant timeline:

1. The principle investigator will screen the potential patients through careful clinical examination of patients at the orthodontic department, Faculty of Oral and Dental Medicine, Future University in Egypt.
2. All recruited patients should fulfil the previously mentioned inclusion and exclusion criteria.
3. Every participant will be asked to sign an informed consent before the beginning of the study.
4. After patient's enrolment, each participant will be asked for pre-intervention records to ensure proper diagnosis.
5. The principle investigator will randomly allocate the patients to one of the intervention groups.

6. Anchorage will be secured by placement of miniscrew, followed by extraction of the first premolar.
7. Active intervention will begin after proper levelling and alignment of the upper arch.
8. The principle investigator will take pre-retraction records for every participant T0.
9. Power chain is used for anterior segment retraction.
10. Each patient will come every 4 weeks for follow up visit, for appliance activation and uptake of impression for interim records + monitoring of recording the VAS sheet.
11. After complete space closure, the principle investigator will take post-retraction records for each participant T1.
12. Every patient will fill up a questionnaire regarding his experience during treatment.
13. The principle investigator will continue the normal treatment and achieve proper finishing for every patient after the end of the study.

F] Sample size calculation:

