Assignment to either intervention will occur before levelling and alignment stage.

D] Blinding:

Blinding of the operators: Blinding will not be possible for the operators during the application interventions and during the follow up visits. The principal operator is responsible for assigning subjects to interventions according to the concealed allocation, appliance activation at follow up visits, dental impressions and acquisition of dental casts.

Blinding of the outcome assessors: It is a single blinded study, therefore, only the outcome assessors will be blind. The patients name will be sealed from pre and

post radiographs and study models. Then two assessors will carry out, blindly and independently, the measurements and analysis of the study.

III) Data collection, management and analysis:

A] Data collection methods:

Primary outcomes:

1. Total Retraction Duration: to assess the timing of antero-posterior movement of anterior teeth and first molars, the principle investigator will take study models for every participant monthly during the follow up visits. Then will digitize the models and identify the landmarks, reference lines and planes on the pre, interim and post-retraction digital dental models for measurements reading. Also, by identifying the landmarks, reference lines and planes using CBCT taken before and after the completion of retraction.

Secondary outcome:

1. Anchorage loss: will be accessed by the principal investigator via CBCT taken before and after the completion of retraction by identifying the landmarks, reference lines and planes, then will interpret the measurements in degrees and millimeters.

2. Pain: Each patient will fill a questionnaire regarding his treatment experience in a VAS scoring from 1-10. The questionnaire will include several questions related to oral hygiene, pain and discomfort experienced throughout the trial.

B] Data management:

A colleague outside the research team will enter the data and organize it in excel sheets in the computer of the orthodontic department.

Data will include all photographs, models, radiographs and filled questionnaire.

C] Statistical Analysis:

- The principle investigator will be responsible for the extraction of the required data from the CBCT taken before and after retraction as well as the study models taken at every follow up visit. The data will be sent to a specialized statistician.

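### The protocol gives the measurements both to two blinded assessors and to the principal investigator, who knows the arm; the conflict is explicit for anchorage loss and likely for the model readings

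*Combined protocol and SAP*

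**What the plan says.** **Blinding (II) D]).** Only the outcome assessors are blind. Patient names are hidden on radiographs and models, and "Then two assessors will carry out, blindly and independently, the measurements and analysis of the study". The Assessors Reliability section also works from the readings of two assessors.

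**Data collection (III) A]).** For the first secondary outcome: "Anchorage loss: will be accessed by the principal investigator via CBCT taken before and after the completion of retraction". The sentence goes on to have this person place the landmarks and interpret the results in degrees and millimetres. For the primary outcome, the principal investigator takes models monthly. The next sentence, which has no subject, reads: "Then will digitize the models and identify the landmarks, reference lines and planes on the pre, interim and post-retraction digital dental models".

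**Statistical analysis (III) C]).** "The principle investigator will be responsible for the extraction of the required data from the CBCT taken before and after retraction". The same sentence extends this responsibility to the models from each monthly visit. The data then go to the statistician.

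**Knowledge of the arm (I) E], Participant timeline).** Item 5: "The principle investigator will randomly allocate the patients to one of the intervention groups". Items 8 and 11 have the principal investigator take the T0 and T1 records, and item 13 has the same person continue treatment.

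**The concern.** Placing landmarks on a CBCT or a digital model involves judgement, and assessor blinding is the only blinding this trial has. If the person who allocates patients and takes their records also produces the readings that are analysed, that protection is gone for those readings. Sealed names and the coded IDs of V) D] conceal nothing from someone who has handled each patient's records.

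Expectations that could colour a reading are written into the Rationale. En-masse retraction is expected to be the better option because it is done in one step, yet it is also thought to carry more risk of anchorage loss. The first could pull readings one way and the second the other.

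The planned reliability work would not show the problem. The 1 mm comparison, the ICC, the kappa and the supervisor's review of variation compare the assessors with each other or with themselves. No text applies any of them to readings by the principal investigator.

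**Working it through.** **Step 1. Who does what, side by side.**

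| Task | II) D] and Assessors Reliability | III) A] and C] |
|---|---|---|
| Anchorage loss on CBCT: landmarks and interpretation | Two blinded assessors | Principal investigator, named |
| Data extraction from CBCTs | Two blinded assessors, as part of the measurements | Principal investigator, named as responsible |
| Data extraction from follow-up models | Two blinded assessors, as part of the measurements | Principal investigator, named as responsible |
| Landmarks on pre, interim and post models | Two blinded assessors, as part of the measurements | No subject; the previous sentence is about the principal investigator |

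For anchorage loss the two columns cannot both hold unless a second, masked reading is meant. No text says so, and none says whose readings are analysed. For the models, being responsible for extraction could mean compiling the assessors' readings, and the landmarking sentence could describe preparation. There the conflict is probable rather than explicit.

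**Step 2. Does the principal investigator know the arm?** Yes, on items 5, 8, 11 and 13 of I) E]. II) C] and II) D] give allocation to the main or principal operator instead, and no section says that this is the same person. The conclusion does not depend on that, because I) E] names the principal investigator directly.

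**Step 3. Illustration of size.** The documents give no SD and no target difference for anchorage loss, so there is no figure of the plan's own to reproduce on this outcome. The arm sizes come from I) F]: 10 per group, raised to 15 for dropout. The 10 reproduces from the stated difference of 1.0 and SD of 0.76: 2 × (1.96 + 0.842)² × 0.76² / 1.0² = 9.07, rounded up to 10. The t-test power at 10 per group is 0.795.

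Assume no true difference, a constant reading shift *s* in one arm only, a common SD, and an unpaired two-sided t-test at 0.05. The Statistical Analysis section names a paired t-test for the group comparison and does not state sidedness. An unpaired test is assumed here because the arms are parallel.

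Noncentrality: δ = s / (SD × √(2/n)), with 2n − 2 degrees of freedom. The false-positive rate is P(|T| > t₀.₉₇₅), where T has a noncentral t distribution with parameter δ.

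At n = 10: √(2/10) = 0.447, 18 degrees of freedom, critical value 2.101.

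| SD (mm, assumed) | s = 0.25 mm: δ, rate | s = 0.5 mm: δ, rate |
|---|---|---|
| 0.5 | 1.118, 19% | 2.236, 56% |
| 1.0 | 0.559, 8% | 1.118, 19% |
| 1.5 | 0.373, 6% | 0.745, 11% |

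At n = 15 and SD 1.0 mm the rates are 10% and 26%. A larger sample makes a fixed reading bias more likely to appear significant.

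For scale, the study of adult Class I women summarised in the Literature Review reports about 1 mm of anchorage loss per 4 mm of incisor retraction. A shift of 0.25 to 0.5 mm would be a quarter to a half of each such millimetre.

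**The case against.** **The investigator may only be preparing records.** The sections could be meant to work together, with the investigator collecting and organising material and the assessors measuring. This stands as a possible reading for the models. It does not fit the anchorage-loss sentence, which names the investigator and includes interpreting the measurements.

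**The illustration does not size the problem.** This also stands. Every SD and shift is assumed, and at 10 per arm the results run from 6% to 56%. The contradiction is in the text and does not rest on these figures.

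**Reliability checks exist.** They do, and there are several. A reader might infer that the 1 mm comparison is the only safeguard and that it would let smaller shifts through. The protocol also plans an ICC, kappa, training and a review of variation. The sound point is narrower: none of these is applied to the principal investigator's readings.

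**Stronger readings that the documents do not support.**
- *All data are extracted unblinded.* III) C] covers CBCTs and study models. Pain is completed by the patient, and a colleague outside the research team enters the data.
- *The primary outcome is shown to be read unblinded.* No section says who dates T0 and T1. The investigator takes both sets of records, but the assessors may be meant to date closure from the models.
- *The bias favours en-masse.* The Rationale's expectations point in different directions for duration and for anchorage loss.

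**Conclusion.** The contradiction is real. For anchorage loss on CBCT it is explicit: if III) A] and C] are followed, the readings come from someone who knows the arm, and the stated assessor blinding does not apply. For the digital-model readings, which also feed the primary outcome, the same conflict is likely but rests on inference from loosely worded sentences.

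The effect on the results cannot be sized from the documents, and no single direction of bias is established. The rates shown assume no true difference, a shift confined to one arm, SDs that the protocol does not give, and an unpaired two-sided test. They show only that shifts of a fraction of a millimetre can matter at these arm sizes when the SD is small. The passages should be reconciled before any record is read.

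**What to change.** In III) A] and III) C], state that the two blinded assessors already planned in II) D] identify the landmarks and take every CBCT and digital-model reading that is analysed. Say that interim models are included. Records should carry only a coded ID and be read in random order.

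Limit the principal investigator to taking the records and passing them on in coded form, and send the assessors' readings to the statistician. The Assessors Reliability section then applies to the readings that are actually analysed.

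**Cost.** No extra staff. Reading time rises, but II) D] already implies most of it. With 30 patients and two CBCTs each, every assessor would read 30 × 2 = 60 CBCTs if CBCT is kept, plus the monthly models.

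**Limit.** Interim two-step models stay partly recognisable, because the Rationale notes a space that persists after canine retraction. Coding cannot fully mask those.

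**Separate points, to be reconciled in their own right.** These are whether anchorage loss is read from digital models (outcome table, Retraction records) or CBCT (III) A]), whether T0 is the same event in both arms, and which event ends retraction. Blinding does not cure them, and this point does not depend on them.

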6. Minimal crowding 2-3 mm.

Exclusion Criteria: for the involved subjects included:

1. Patients suffering from any systemic diseases interfering with tooth movement.
2. Patients with extracted or missing permanent teeth. (Except for third molars).
3. Patients with badly decayed teeth.
4. Patients with any parafunctional habits (i.e. Bruxism, tongue thrusting, mouth breathing, etc...).
5. Patients with previous orthodontic treatment.

C] Interventions:

➤ Medical History Questionnaire:

For every patient, to exclude the presence of any systemic condition interfering with orthodontic treatment.

➤ Clinical Examination:

Oral structures will be examined to identify caries, fracture or missing teeth. Gingival tissues will be carefully examined for any gingivitis, periodontitis, recession, or lesions.

➤ Diagnosis

Check the potential patient to fulfill the previously mentioned inclusion criteria. Every participant will be asked to sign an informed consent about the study. Full set of records (study models, panorama radiograph and lateral cephalometric radiographs, photos) will be taken for every patient as part of the routine procedure for treatment of patients in the clinic of the Orthodontic Department, Future University in Egypt.

➤ Clinical Procedure:

After taking pre-treatment records, every patient will receive:

- Miniscrews will then be placed in the upper arch between the second premolar and first molar.
- The patient will be referred for extraction of first premolars.

- Anchorage will be secured, followed by Leveling and alignment for the bonded and banded teeth through following the wire sequence: 0.014 NiTi, 0.016×0.022 NiTi and 0.017×0.025 StSt.
- Bonding of all teeth except for first premolars and banding/bonding the first and second molars will be done using Roth prescription brackets (0.022 x 0.028 slot)*.
- After leveling and aligning is completed (right before retraction), the patient will be referred for the uptake of pre-intervention records for en masse group (Impression for models, photos extra oral and intra oral and pain questionnaire).
- For two step group canine retraction will take place on a 0.017×0.025 StSt arch wire, once canine retraction stage is completed, the patient will be referred for the uptake of pre-intervention records.

➤ **Acquisition of pre-intervention records:**

- Alginate impressions will be taken before retraction (without the arch wire in place) followed by digital scanning of produced models.

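### The two-step arm's T0 can be read as before or after canine retraction, and anchorage loss has two measuring tools with neither governing

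*Combined protocol and SAP*

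**What the plan says.** **Timing of T0.** Section I) D] Outcomes gives a general rule: "All outcomes will be assessed as the difference between T0 at the start of retraction and T1 after complete space closure". The participant timeline (I) E], item 8) adds: "The principle investigator will take pre-retraction records for every participant T0". That item follows levelling and alignment (item 7) and precedes the power chain (item 9).

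The Clinical Procedure in I) C] times the records by arm. For en-masse: "After leveling and aligning is completed (right before retraction), the patient will be referred for the uptake of pre-intervention records for en masse group". For two-step, canine retraction comes first, and then "once canine retraction stage is completed, the patient will be referred for the uptake of pre-intervention records". No earlier pre-retraction record is itemised for the two-step arm. This section does not use the label T0.

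**Duration.** III) A] names the primary outcome as "Total Retraction Duration: to assess the timing of antero-posterior movement of anterior teeth and first molars", with landmarks read from pre, interim and post models and from CBCT. The Outcome measure table also lists dated visit records as a source.

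**Anchorage loss.** The Outcome measure table gives digital models, linear, in mm. Retraction records in I) C] also take molar anchorage loss from the final dental model, without a unit. III) A] differs: "Anchorage loss: will be accessed by the principal investigator via CBCT taken before and after the completion of retraction", read in degrees and mm. III) C] Statistical Analysis extracts data from both CBCT and models. No section ranks them.

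**The concern.** Canine retraction is the first of the two steps under comparison. A baseline taken after it would measure the en-masse arm over its whole retraction and the two-step arm over its second stage only. The en-masse arm loses nothing, so the error would run one way: less apparent anchorage loss and, depending on how the clock is started, a shorter apparent duration in the two-step arm. Duration is the primary outcome and the research question. Because the T0 to T1 rule covers all outcomes, anterior tooth position and root resorption would be affected as well.

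The anchorage tool is a separate matter. Both sources will be extracted, so two anchorage results can exist, and without a governing definition the choice between them can be made after the data are seen.

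**Working it through.** **1. The plan's own figure.** Inputs from I) F]: difference 1.0, SD 0.76, power 0.8, alpha 0.05 (two-sided assumed). Normal approximation: n = 2 × [0.76 × (1.960 + 0.842)]² / 1.0² = 9.07, rounded up to 10 per group. This reproduces the stated 10. Exact two-sample t-test power is 0.79 at 10 per group and 0.94 at the 15 recruited. The T0 question does not alter this calculation. It alters what difference the trial would observe.

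**2. T0, side by side.**

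| Source | En-masse | Two-step |
|---|---|---|
| I) D] Outcomes | start of retraction | start of retraction |
| I) E] items 7–9 | after levelling, before power chain | same, canine stage not mentioned |
| I) C] Clinical Procedure | after levelling, right before retraction | after canine retraction |

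The first two rows allow a common T0 before any retraction. In the third, the only itemised two-step baseline follows part of the retraction. The subsection on beginning retraction comes after these records, which favours reading them as T0, but the text does not say so.

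**3. Can the 4-weekly models fill the gap?** I) E] item 10 says "Each patient will come every 4 weeks for follow up visit, for appliance activation and uptake of impression for interim records", and III) A] will "identify the landmarks, reference lines and planes on the pre, interim and post-retraction digital dental models for measurements reading". These could capture part of the canine stage. However, I) C] lists the visits after the start of retraction, and no section says that they begin with canine retraction or that one of them serves as T0.

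**4. Illustration for duration**, only if the post-canine records start the clock. Assumptions: 1.0 and 0.76 are months (I) F] gives no unit), the two-step arm is truly 1.0 month longer, and k 4-week intervals are omitted (the canine-stage length is not given). Four weeks = 28 / 30.44 = 0.92 month. Observed difference = 1.0 − 0.92k. The probabilities are for a significant two-sided t-test (SD 0.76) showing the two-step arm longer.

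| k | Observed difference (months) | 10 per group | 15 per group |
|---|---|---|---|
| 0 | 1.00 | 0.79 | 0.94 |
| 1 | 0.08 | 0.04 | 0.05 |
| 2 | −0.84 | <0.001 | <0.001 |

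**5. Illustration for anchorage.** Under-reading in the two-step arm = L × f, where L is total molar loss and f is the share occurring during canine retraction. The documents give neither for this trial. The literature review reports about 1 mm of molar loss per 4 mm of incisor retraction in one cited comparison. With L = 1 mm and f assumed at 0.25 to 0.75, the under-reading is 0.25 to 0.75 mm; with L = 0.5 mm it is 0.125 to 0.375 mm; with L = 0 it is 0. The protocol's description of that comparison mentions no miniscrews, whereas this trial uses them in both arms, so zero is a real possibility.

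**6. CBCT baseline.** III) A] and III) C] rely on a CBCT before retraction. The itemised record lists in I) C] contain models, panoramic and lateral cephalometric radiographs, photographs and a pain questionnaire, but no CBCT before retraction. The only CBCT there is the final one, for the anterior teeth.

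**The case against.** The strongest reply is that the Clinical Procedure never calls its records T0, while I) D] and I) E] put T0 at the start of retraction for everyone. On that reading both arms share a baseline. A reader might infer from the Clinical Procedure that the plan definitely excludes the canine stage. The documents do not support that: they leave T0 open. Nor do they settle it the other way, because the timeline never mentions canine retraction and its item 9 refers only to the anterior segment.

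Second, duration need not depend on a model. The Outcome measure table lists dated visit records, and III) A] speaks of total retraction duration. The canine stage could be recovered from those dates, so it would be too strong to say that the primary outcome is biased as planned. But no section says which date starts the clock, and visit dates cannot restore a tooth position that was never recorded.

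Third, the follow-up visits give the two-step arm its own force figure, which may hint that those visits cover canine retraction. This is suggestive only.

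Fourth, a reader might infer that no CBCT before retraction is planned at all. The wording points the other way: Retraction records refer to the same radiology centre and to a final scan, and II) D] Blinding mentions radiographs from before and after. An omission from the lists is the likelier explanation.

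Finally, the magnitudes rest on assumed inputs. That is correct. They show how sensitive the result could be, not how large any bias is.

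**Conclusion.** The inconsistency stands on the text in two parts. T0 in the two-step arm is undefined as between before and after canine retraction, and anchorage loss has two tools and sets of units with neither governing. If the post-canine records serve as T0, movement during canine retraction is lost from every T0 to T1 change in the two-step arm and in no other. That understates its anchorage loss to the extent that the molars move during that stage. Its duration is also shortened unless the clock is taken from visit dates. If T0 precedes canine retraction in both arms, this bias does not arise.

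The size is illustrative. Under the months assumption, one omitted 4-week interval nearly removes a true 1.0-month difference and two reverse its sign. The assumed anchorage range is 0 to 0.75 mm. Confidence is high in the inconsistencies; the bias itself is conditional. The point should be resolved before enrolment, because a missed baseline impression cannot be taken later.

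**What to change.** - State one T0 for both arms: the end of levelling and alignment, before any retraction, which in the two-step arm means before canine retraction. Take the T0 impression and scan then, and count duration from that visit date in both arms.
- Keep the two-step arm's model after canine retraction as an interim record, and start the 4-weekly models at T0 in both arms.
- Reconcile T1, defined in I) D] by complete space closure, with the four criteria for ending retraction in I) C].
- Name one governing tool and unit for anchorage loss before any data are seen, with the other supportive. Either is defensible; models in mm need no added imaging.
- Reconcile the record lists in I) C] with III) A] and III) C] on the CBCT before retraction, adding no imaging that is not already planned.

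**Cost.** At most one impression and scan for each of the 15 planned two-step patients, which item 8 of the timeline arguably already requires, plus wording. If models govern, CBCT molar angulation becomes supportive.
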